#### **4.3 *Withdrawal Of Subjects***

At any time during the study, a subject may discontinue (i.e., withdraws consent or is no longer willing to participate) or a subject may be withdrawn by the Investigator because of a safety risk, adverse event, or noncompliance. The reason for early withdrawal shall be noted in the appropriate CRF.

The Sponsor has the option to enroll additional subjects to replace subjects who discontinue prematurely.

#### **4.4 *Study Termination***

Eiger BioPharmaceuticals may terminate the study if new findings indicate that the study would be potentially dangerous or detrimental to subjects. Eiger BioPharmaceuticals may also terminate the study for administrative reasons unrelated to the purpose of the study. In addition, the regulatory agency or the site's IRB/EC has the authority to stop the study.

### **5 STUDY TREATMENT**

#### **5.1 *EBP-994***

The drug to be utilized for this study is EBP-994 (previously developed as lonafarnib by Schering-Plough, now Merck). The EBP-994 active pharmaceutical ingredient (API) is manufactured by Schering Corporation located in [name]. Each capsule contains 25 mg, 50 mg or 75 mg of EBP-994.

##### **5.1.1 *Description of EBP-994***

[figure not shown]
**IUPAC Name:** 4-(2-4-[(11R)-3,10-dibromo-8-chloro-6,11-dihydro-

*5H*benzo[5,6]cyclohepta[*b*]pyridin-11-yl]piperidino-2-oxoethyl)-1-piperidinecarboxamide

**CAS Number:** none

**Molecular Formula:** C27H31N4O2ClBr2

**Molecular Weight:** 638.7 g/mol

**Figure 4: EBP-994**

### 5.1.2 Description of Study Treatment

Study Visit 2 (Day 1) marks the initiation of the Treatment Period; all subjects will begin dosing with EBP-994 alone or in combination with Norvir® and/or Pegasys®, and continue dosing through Study Visit 7, 8, 9, 10, 11-47 (depending on treatment duration) morning dose.

#### 5.1.2.1 Dosage Form of EBP-994

EBP-994 is formulated into hard gelatin, white opaque capsule shells. Each capsule contains 25 mg, 50 mg or 75 mg of EBP-994. The capsules are provided in white opaque high density polyethylene (HDPE) bottles with polypropylene twist off caps and desiccant. Each bottle contains 30 capsules. EBP-994 is stable if stored at 20°C - 25°C (68°F - 77°F). A “use by” date is included on the product label. EBP-994 should be stored at room temperature 20°C - 25°C (68°F - 77°F) in a locked, limited-access storage area prior to dispensing.

#### 5.1.2.2 Dosage Form of Ritonavir

Commercial formulation of ritonavir (Norvir®) is supplied as 100-mg, white, film-coated, ovaloid tablets in white, opaque, HDPE bottles with polypropylene twist-off caps.

Ritonavir should be stored at or below 30 °C (86 °F).

#### 5.1.2.3 Dosage Form of Pegylated Interferon

Commercial formulation of Pegasys® is supplied in vials. Each vial contains approximately 1.2 mL of solution to deliver 1.0 mL of drug product. Subcutaneous (SC) administration of 1.0 mL delivers 180 µg of drug product (expressed as the amount of interferon alfa-2a). The solution is colorless to light yellow.

## **5.2 Administration**

Subjects will be instructed to self-administer EBP-994 at 8, 12 or 24 hour intervals  $\pm 2$  hours. Norvir® at 12 or 24 hour intervals  $\pm 2$  hours and/or Pegasys® at weekly intervals . If a dosing window is missed, the subject should skip the dose completely. Subjects should not “double up” at the next scheduled dose period.

## **5.3 Concomitant Medications**

All drugs that are listed as excluded in the Exclusion Criteria should not be initiated during the study unless prior approval has been received from the Medical Monitor. Check the prescribing information of Norvir® and Pegasys® before initiating any concomitant medication.

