### **Safety**

Safety will be monitored by assessing vital signs, adverse events, concomitant medications and laboratory and ECG results. ECGs will be conducted in triplicate and vital signs assessed at each Study Visit.

The most common side effects seen with lonafarnib (the active ingredient of EBP-994) are gastrointestinal (diarrhea, nausea, and vomiting). There were no serious adverse events (SAEs) observed in the studies conducted in healthy volunteers. The SAEs reported in at least 2% of subjects in the Phase 1 and Phase 2 studies conducted in subjects with solid tumors or hematologic malignancies included fever (6%), diarrhea (6%), dehydration (6%), febrile neutropenia (4%) and sepsis (4%).

As with any anti-viral medication, a possible effect of EBP-994 is viral resistance. Hepatitis D viral load levels will be measured through quantitative PCR at all Study Visits. Viral mutation analysis and resistance phenotyping will be conducted to assess viral resistance to the study medication. The investigator may terminate the subject from the trial if, in his/her opinion, there is an unacceptable increase in HDV viral load. Moreover, the investigator is free to initiate standard of care (SOC) medications and doses (i.e. Pegasys®) at any time point.

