### **Clinical Safety Summary**

There are currently no HDV-specific therapies. EBP-994 could be the first direct acting anti-HDV agent by disrupting the HDV life cycle through inhibition of prenylation at the level of host cell farnesyl-transferase. EBP-994 has been dosed in human studies examining PK and PD and has exhibited inhibition of farnesyl transferase at levels below the maximally tolerated dose (MTD; 300 mg BID). A risk associated with the use of direct acting antiviral agents would be the development of resistance by the virus. However, because prenylation is a host function not coded for by the HDV genome, the risk of resistance development could be mitigated. Viral surveillance will be conducted throughout the conduct of the study to assess the risk of viral resistance. Two doses of EBP-994 alone, or in combination with Norvir® and/or Pegasys® will be examined in this proof-of-concept study, 200 vs. 300 mg

(PO BID), and the adverse profile will be correlated to the clinical benefit of viral suppression.

Other risks that may be encountered with the treatment of HDV include an increase in liver function tests during and after therapy, the risk of a flare in HBV ( $\geq 1$  log increase in HBV viral load) as the HDV viral load goes down, and an increase in HDV viral load after therapy is ended. Flares in liver function tests are not uncommon with the start of treatment of HBV disease and necessitate a careful and frequent review of liver function studies. We will follow the same approach in this study unless there is a concomitant flare in HBV viral load. A flare of HBV viral load while on EBP-994 will be treated by starting specific anti-HBV therapy using one of the 5 approved drugs, the selection being made by the Investigator based on the subject's condition and history of prior anti-HBV therapy. A flare in HDV viral load after the termination of EBP-994 will be watched closely and interferon therapy may be started as determined by the investigator.

Finally, the known adverse event profile for EBP-994 (and all other prenylation inhibitors in clinic) is primarily gastrointestinal, primarily dose related diarrhea as well as nausea and vomiting.

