## 2 STUDY OBJECTIVES

The primary objectives of the study are to:

- Evaluate the safety and tolerability of 12 weeks of treatment with either a 200 mg po BID dose of EBP-994, or a 300 mg po BID dose of EBP-994, in subjects chronically infected with HDV genotype 1
- Evaluate the pharmacodynamic (PD) activity of a 200 mg po BID dose of EBP-994, vs. a 300 mg po BID dose of EBP-994 on HDV viral load
- Evaluate the pharmacokinetic (PK) profile of a 200 mg po BID dose of EBP-994 vs. a 300 mg po BID dose of EBP-994 in subjects chronically infected with HDV genotype 1
- Evaluate the safety, tolerability, PK, and HDV viral load of a treatment up to 48 weeks with EBP-994 alone, or in combination with Norvir® and/or Pegasys® in subjects chronically infected with HDV

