## **8.2 *Analysis Populations***

The Safety Population comprises all subjects who are enrolled and receive at least one dose of study drug, and who have at least one post-dosing safety evaluation. All safety endpoints will be analyzed using the Safety Population.

The Per-Protocol Population comprises all subjects who complete at least Study Visit 4, as specified in the protocol. All pharmacodynamic analysis will be conducted using the Per-Protocol Population.

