### **8.6 Pharmacodynamics**

Listings will display viral load data at each period/timepoint collected by subject and these data will be presented graphically. Mean and median levels of the viral load will be calculated at each period/timepoint.

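### Viral loads taken after Pegasys is added in Group 1 or 2 stay in the same means and medians, which then no longer describe EBP-994 alone or with Norvir

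*Combined protocol and SAP*

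**What the plan says.** **Permission.** The Safety paragraph of the Protocol Summary states that "the investigator is free to initiate standard of care (SOC) medications and doses", gives Pegasys as what is meant, and allows this at any time point. It attaches no viral load threshold. Similar sentences about licensed medications stand in the synopsis (Study Design and the dosing plan summary), in Section 3 (twice) and in Section 7.3. Those sentences go on to mention lowering the EBP-994 dose and end with gastrointestinal side effects as the ground.

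**Approval.** Section 5.3 says that drugs excluded at entry "should not be initiated during the study unless prior approval has been received from the Medical Monitor". Exclusion 13 of Section 4.2 covers immune modulating agents as a class and does not name Pegasys.

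**Groups.** In both the synopsis and Section 6.2, Group 1 is EBP-994 monotherapy and Group 2 is EBP-994 with Norvir. Neither includes Pegasys by assignment.

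**Analysis.** Section 8.2: "The Per-Protocol Population comprises all subjects who complete at least Study Visit 4", which Section 6.4 places on Day 3, and "All pharmacodynamic analysis will be conducted using the Per-Protocol Population". Section 8.6 plans listings by subject and graphs, and adds: "Mean and median levels of the viral load will be calculated at each period/timepoint". Section 8.9 deals only with missing values.

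**Objective.** The fourth primary objective in Section 2 includes "HDV viral load of a treatment up to 48 weeks with EBP-994 alone, or in combination" with Norvir and/or Pegasys.

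**The concern.** The group label fixes what a viral load summary is taken to describe. If a subject in Group 1 or 2 starts Pegasys, that label no longer matches the treatment received, but the plan goes on using the subject's values as before. Nothing in Sections 8.2, 8.6 or 8.9 excludes, flags or separates them.

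The means and medians are the only numerical viral load summaries planned. If some of the values behind them come from subjects who have moved to a Pegasys regimen, a reader cannot tell how much of a fall seen under EBP-994 alone, or under EBP-994 with Norvir, belongs to that regimen.

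**Working it through.** **1. Following one subject through the text**

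| Step | Group 1 subject | Group 2 subject |
|---|---|---|
| Assigned regimen | EBP-994 | EBP-994 + Norvir |
| After Pegasys is added (synopsis, Safety) | EBP-994 + Pegasys | EBP-994 + Norvir + Pegasys |
| In the Per-Protocol Population (8.2)? | Yes, if Visit 4 was completed | Yes, if Visit 4 was completed |
| Later values in the means and medians (8.6)? | Yes | Yes |

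An approved start and an unapproved start give the same last two rows, so Section 5.3 does not affect the result.

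**2. How many visits can be touched**

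Viral load is measured at all study visits. If Pegasys could start as early as Day 1, the exposed visits for a 48-week subject are Visits 3 to 18 plus Visit 19: 16 + 1 = 17. For a 4-week subject they are Visits 3 to 7 plus Visit 19: 5 + 1 = 6. A later start exposes fewer. Separately, Section 1.2 says that for an HDV flare after EBP-994 has ended, "interferon therapy may be started as determined by the investigator"; that can affect the follow-up value only.

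**3. Possible size (illustration on assumptions)**

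The plan has no figure of its own to reproduce. Section 8.7 states no expected effect or variability, and no allocation ratio or rate of Pegasys addition is given.

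Assumptions: all 75 subjects enrolled and split equally, 75/4 = 18.75, taken as n = 19; summaries made by group on the log10 scale; k subjects have Pegasys added; each then has an extra fall of d log10, fully present at the visit summarised.

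Shift in the group mean = k × d / n.

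| k | k/19 | d = 0.5 | d = 1 | d = 2 |
|---|---|---|---|---|
| 1 | 5.3% | 0.026 | 0.053 | 0.105 |
| 2 | 10.5% | 0.053 | 0.105 | 0.211 |
| 4 | 21.1% | 0.105 | 0.211 | 0.421 |

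A partial effect at a given visit gives proportionally less. If Pegasys goes to the k subjects with the highest viral loads, the median moves less than the mean. A simulation with normal values, SD 1 and d = 1 gives 0.003, 0.018 and 0.102 log10 for k = 1, 2 and 4.

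**4. Why leaving the later values out is not enough on its own**

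If those k subjects are the ones with the highest values, dropping them also lowers the mean. For 19 normal values, removing the highest 1, 2 or 4 lowers it by about 0.10, 0.19 or 0.35 SD. Each version can mislead, so both are needed.

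**The case against.** The case on the other side has real force.

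- **The permission is narrower than it looks.** The five sentences on licensed medications end in a clause about gastrointestinal side effects. If that clause governs the whole sentence, they may concern only treatment of those effects. This stands: they may allow Pegasys, but the clear permission rests on the one synopsis sentence. Section 3's own paragraph on resistance does not repeat it.
- **Who receives Pegasys is not stated.** A reader might infer that it goes to the poorer responders, because the permission follows a sentence on an unacceptable rise in HDV viral load. That earlier sentence offers a different remedy, ending the subject's participation, and no viral load trigger is attached to Pegasys. The selection is plausible, but the documents do not state it.
- **No contrast between groups is planned.** A reader might infer that a comparison with Groups 3 and 4 would be diluted. Section 8.6 contains no such comparison and does not even say that the summaries are by group. The EBP-994 ceilings in Section 6.2 (600 mg daily in Group 1, 200 mg in Group 3) would also prevent a clean reading of the Pegasys effect.
- **The data can be traced.** Viral loads are listed by subject, and concomitant medications are recorded at every visit. This stands as mitigation, but tracing individual values does not correct the means and medians.
- **This is an open-label pilot, and keeping all observed values is defensible.** Agreed. The remedy keeps that summary and adds a second one.

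**Conclusion.** The point holds in a limited form. The synopsis permits Pegasys to be added in Groups 1 and 2, and Sections 8.2 and 8.6 leave the later viral loads in the same summaries. Where this happens, those summaries no longer describe EBP-994 alone or with Norvir, as the fourth primary objective intends.

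The size is unknown. The range of 0.03 to 0.42 log10 depends wholly on the assumed group size, number of additions and effect. The direction is probably toward lower viral loads, provided that Pegasys is active in these subjects.

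A reader might also infer that Section 5.3 contradicts the permission. The documents do not establish this. Section 5.3 can sensibly be read as the specific rule, and whether added Pegasys counts as an excluded immune modulating agent is left open. Clearer wording there is optional, and the point does not depend on it.

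This is an inexpensive improvement to the reporting and does not call the design into question.

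**What to change.** Add to Section 8.6:

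1. Record the start date of any Pegasys added in Group 1 or 2.
2. Flag the affected subjects in the listings and graphs, and give their number at each visit.
3. Present viral load means and medians by group in two versions: all observed values, and without values after the Pegasys start. State beside the second version that it may drop poorer responders.

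The cost is one flag, one extra summary and one date field to confirm, since the protocol does not say that start dates of concomitant medications are captured. The investigator's clinical freedom is unchanged. Clarifying Section 5.3 for Pegasys, QT-prolonging drugs and anti-HBV therapy would be tidy but is not needed for this point.

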## **5.4 Measuring Subject Compliance**

Study drug is administered on an out-patient basis. Subjects will be instructed to return all study drug containers dispensed at the previous study visit (including empty ones) at each Study Visit in order to measure study drug compliance. The study coordinator will verify the subject has taken the correct amount of study medication prior to issuing the next supply of study medication.

## **5.5 Drug Accountability**

All supplies of study drug will be accounted for by study personnel in accordance with current Good Clinical Practices (GCPs). Details of receipt, storage, administration, and return or destruction of study drug will be recorded in the study drug accountability record according to the standard operating procedure of the investigational site. Copies of the study drug accountability record will be provided to the Sponsor.

# **6 STUDY PROCEDURES**

Refer to Appendix 1 for Schedule of Events.

## **6.1 Screening; Visit 1**

The outpatient Screening Visit must occur no more than 21 days prior to Study Visit 1. Written informed consent must be given before any study related diagnostic or screening procedures. At the Screening Visit, subjects will have all required evaluations to determine their eligibility to participate in the study as follows:

1. Written informed consent
2. Medical history

3. Comprehensive physical examination (performed by a physician) including CTP scoring and encephalopathy assessment (see Appendix D)
4. Weight and height (BMI is based on these measures; see Appendix B)
5. Vital signs (BP after being seated for 5 minutes, pulse, respiratory rate and temperature)
6. List of concomitant medications
7. Serial 12-Lead ECG (x3) 2-3 minutes apart
8. Liver biopsy (if needed)
9. Laboratory studies (non-fasting):
  - a. Serum chemistry panel, including liver function tests and albumin
  - b. Thyroid function tests, T3, T4, TSH
  - c. Complete blood count (CBC with differential and platelet count)
  - d. Quantitative PCR for HCV viral load
  - e. HCV genotype
  - f. Blood samples (plasma and serum) for viral mutation analysis and resistance phenotyping
  - g. Serologies (HCV, and anti-HIV Ab)
  - h. INR
  - i. Urinalysis
  - j. Urine drug screen for opiates, amphetamines, barbiturates, benzodiazepines, cocaine
  - k. Serum pregnancy test (child bearing females only)
  - l. Blood sample for monitoring immunologic changes in peripheral blood mononuclear cells (PBMC).

Subjects meeting all of the inclusion criteria and none of the exclusion criteria and giving written informed consent will return within 21 days after screening for Study Visit 1 when randomization one of the treatment groups will occur.

## **6.2 Study Visit 2 (Day 1) - Treatment Period**

This Study Visit marks the beginning of the twenty-four weeks treatment Period in which subjects will receive EBP-994 treatments (EBP-994 alone or in combination with Norvir® and/or Pegasys®). Subjects will be admitted to the unit on the morning of Day 1 in a fasted

state (nothing to eat or drink except water) and will receive a standard breakfast between 45 - 30 minutes prior to scheduled dosing time.

The following evaluations and procedures will be performed at Study Visit 1 (see Appendix A for summary):

1. Brief physical examination pre-dose (performed by a physician, nurse practitioner, physician's assistant or nurse). This includes weight and vital signs as well as HEENT, heart, lungs, abdomen and lower extremity.
2. Vital signs pre-dose and after the post-dose ECG (BP after being seated for 5 minutes, pulse, respiratory rate and temperature)
3. Concomitant medications will be recorded
4. Adverse events will be recorded
5. 12-Lead ECG
6. Randomization

Subjects will be randomized to one of the following groups:

Group 1: EBP-994 (up to 600 mg daily dose) monotherapy  
Group 2: EBP-994 (up to 200 mg daily dose) in combination with Norvir®  
Group 3: EBP-994 (up to 200 mg daily dose) in combination with Pegasys®  
Group 4: EBP-994 (up to 200 mg daily dose) in combination with Norvir® and Pegasys®

7. Laboratory studies (Pre-Dose) (non-fasting):
  - a. Serum chemistry panel, including liver function tests and albumin
  - b. Complete blood count (CBC with differential and platelet count)
  - c. Quantitative PCR for HDV viral load
  - d. Blood samples (plasma and serum) for viral mutation analysis, resistance phenotyping, and analysis of drug mechanism and treatment response. These analyses include molecular and genetic analysis of drug mechanism, viral/host factors influencing treatment response (e.g. genotype and subgenotype analysis, quasispecies analysis, determination of drug and potential metabolite levels in plasma).
  - e. Urinalysis
  - f. Urine pregnancy test (child-bearing females only)

- g. Blood sample for monitoring immunologic changes in peripheral blood mononuclear cells (PBMC).
- 8. Pharmacokinetic blood samples (at the following time points: 0-pre-dose, post dose: 15 min, 30 min, 60 min, 90 min, 2h, 2.5 h, 3 h, 4 h, ,6 h, 8, 10, 12 h) (for those subjects participating in the PK portion of this trial)
- 9. Dosing Instructions:  
Dosing with EBP-994 alone or in combination with Norvir® and/or Pegasys® should occur after the pre-dose vital signs have been taken, the physical examination performed, the ECG performed and pre-dose lab samples drawn. EBP-994 capsules and/or Norvir® should be taken orally with 240 mL of water. After the morning dosing, the post-dose procedures should be conducted in the following order: ECG, vital signs, post-dose plasma and serum blood samples.

Subjects will be sent home 3 hours post-dose (except for those participating in the PK component of the study) with container(s) of study drug(s) and will be instructed to self-administer study drug(s) at appropriate intervals. Oral study drug should be swallowed with 240 mL of water. Subjects will also be given a diary to record the date, time and number of capsules they take.

Subjects should be instructed to bring all container(s) and any unused study medication to the study site at the next study visit. Subjects should be instructed NOT to take their morning dose of study drug on the morning of the next study visit, Day 2, as pre-dose assessments will be conducted.

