### Study Design

This study is a phase II, randomized, open-label study up to 48 weeks of treatment with EBP-994 alone, or in combination with Norvir® and/or Pegasys® in subjects chronically infected with HDV genotype 1. The duration of the study for each subject will last approximately 11-55 weeks (up to three week screening period, 4-48 week treatment period and four week safety follow-up period. The duration of the entire study is anticipated to be approximately 45 months (first subject in to last subject out). The investigator is free to initiate licensed medications at any time point and decrease the dose of EBP-994 if deemed warranted for GI side effects.

This study will explore EBP-994 in four groups of treatments:

Group 1: EBP-994 (up to 600 mg daily dose) monotherapy

Group 2: EBP-994 (up to 200 mg daily dose) in combination with Norvir®

Group 3: EBP-994 (up to 600 mg daily dose) in combination with Pegasys®

Group 4: EBP-994 (up to 150 mg daily dose) in combination with Norvir® and Pegasys®

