**Figure 3. Average serum EBP-994 concentration vs. average change in HDV viral load over days 7-28 of treatment.**

These data demonstrate: 1) EBP-994 is well-tolerated in patients with chronic hepatitis D infection; 2) a direct antiviral effect of EBP-994 against HDV; 3) a dose dependence of EBP-994's anti-HDV efficacy; 4) suboptimal levels of drug appear to be achieved in this patient population at the relatively low dose (100 mg PO BID) used in this first phase of the study; 5) a strong rationale exists for progressing to the planned higher dose of EBP-994. In addition to using the higher doses of EBP-994 that were previously used and tolerated in generally sicker patients (i.e with advanced malignancies, including metastatic disease and blast crisis), a duration of treatment longer than 28 days is expected to be needed to achieve more profound suppression of HDV viral loads (including to undetectability) that will be maintained upon cessation of treatment (indicative of cure). These are exactly the interventions to be explored in the current study that aims to determine the safety and efficacy of EBP-994 alone, or in combination with Norvir® and/or Pegasys® in chronically infected HDV patients for up to 6 months.

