## 3 STUDY DESIGN

This study is a phase II, randomized, open label study of up to 48 weeks of treatment with EBP-994 alone, or in combination with Norvir® and/or Pegasys® in subjects chronically infected with HDV genotype 1. The investigator is free to initiate licensed medications at any time point and decrease the dose of EBP-994 if deemed warranted for GI side effects. The duration of the study for each subject will be approximately 11-55 weeks (up to three week screening period, up to 48 week treatment period and four week safety follow-up period).

The duration of the entire study is anticipated to be approximately 36 months (first subject in to last subject out). Pharmacokinetic sampling will be done at Day 1 and Day 28 of dosing. PK sampling will be conducted only on subjects who have consented to participate in the PK portion of this study. Participation in PK sampling is optional for each subject.

At the Screening Visit, subjects giving written informed consent will have all required evaluations to determine their eligibility to participate in the study. The outpatient screening visit must occur within 21 days of Study Visit 1.

Each eligible subject will undergo 8-16 Study Visits; Screening, Day 1, Day 2, Day 3, Day 7, Day 14, Day 28, then every 4 weeks (total duration depends on assigned treatment group), followed by a Safety Follow-Up Visit, 4 weeks post-treatment. Study drug will consist of EBP-994 alone or in combination with either Norvir® and/or Pegasys®, depending on which group the subject has been randomized to on the Day 1 visit. Moreover, the investigator is free to initiate licensed medications at any time point and decrease the dose of EBP-994 if deemed warranted for GI side effects.

During the intervals between Study Visits, subjects will be free to carry on their usual activities of daily living. Subjects will be instructed to take their study medication at appropriate dosing intervals. Efforts should be made to schedule Study Visits according to the study protocol; however the window for consecutive Study Visits will be  $\pm 2$  days with the exception of Day 2 and Day 3 for which a visit window is not allowed.

Safety will be monitored by assessing vital signs, adverse events, concomitant medications, laboratory and ECG results. ECGs will be conducted and vital signs assessed at each Study Visit.

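### The maximum EBP-994 daily dose conflicts for two of the four randomised groups: Group 3 (600 vs 200 mg) and Group 4 (150 vs 200 mg)

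*Combined protocol and SAP*

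**What the plan says.** Two current lists define the groups.

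- **Protocol Summary, Study Design:** Group 1 up to 600 mg/day and Group 2 (with Norvir) up to 200 mg/day; then "Group 3: EBP-994 (up to 600 mg daily dose) in combination with Pegasys" and "Group 4: EBP-994 (up to 150 mg daily dose) in combination with Norvir® and Pegasys".
- **Section 6.2, item 6 (Randomization):** the same figures for Groups 1 and 2; then "Group 3: EBP-994 (up to 200 mg daily dose) in combination with Pegasys" and "Group 4: EBP-994 (up to 200 mg daily dose) in combination with Norvir® and Pegasys".

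Other sections touch on dose without setting a ceiling by group. Section 3 says that the drug combination is given "depending on which group the subject has been randomized to on the Day 1 visit" and stops there. Section 5.2 covers timing: "Subjects will be instructed to self-administer EBP-994 at 8, 12 or 24 hour intervals". Section 5.1 covers strengths: "Each capsule contains 25 mg, 50 mg or 75 mg of EBP-994". Section 1.2 (Clinical Safety Summary) says that two doses, 200 and 300 mg BID, will be examined, whether EBP-994 is given alone or with Norvir and/or Pegasys. It does not say in which groups.

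**The concern.** A dose ceiling is an instruction that the site acts on. With two ceilings for one numbered group, the protocol does not tell the site whether a given dose is allowed or is a deviation. Section 5.4 asks the study coordinator to verify that the correct amount was taken, and Section 14 asks the investigator to follow the protocol. For Groups 3 and 4 neither can be judged from the text over part of the dose range.

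The stakes run both ways. Section 1.2 describes diarrhoea with EBP-994 as dose related and gives the maximally tolerated dose as 300 mg BID. For Group 3, one page therefore allows that full dose alongside interferon and the other allows a third of it. If the higher figure is the error, subjects may be over-dosed; if the lower figure is the error, they may be under-dosed.

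**Working it through.** The plan has no calculation to reproduce: Section 8.7 gives no statistical basis for the sample size, and none bears on this point. The check sets the two lists side by side and then looks for text that decides between them.

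**Step 1. The ceilings (mg/day).**

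| Group | Combination | Summary | Section 6.2 | Summary minus 6.2 | Higher / lower |
|---|---|---|---|---|---|
| 1 | none | 600 | 600 | 0 | 1 |
| 2 | Norvir | 200 | 200 | 0 | 1 |
| 3 | Pegasys | 600 | 200 | +400 | 600/200 = 3.0 |
| 4 | Norvir + Pegasys | 150 | 200 | −50 | 200/150 = 1.33 |

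Two of four groups conflict. Section 6.2 is lower in Group 3 and higher in Group 4, so neither list is simply the cautious one.

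**Step 2. Doses with no clear status.** Group 3: above 200 and up to 600 mg/day. Group 4: above 150 and up to 200 mg/day. At or below 200 mg (Group 3) or 150 mg (Group 4), a dose satisfies both pages.

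**Step 3. Does the wording reconcile them?** Both lists give maxima, and two different maxima cannot both be the maximum. The investigator may reduce the dose for gastrointestinal effects (Summary and Section 3), but that does not change the ceiling and cannot explain a higher figure in Section 6.2 for Group 4.

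**Step 4. Do the capsules decide?** Taking BID dosing as an example:

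- 150/2 = 75 mg = 1 × 75
- 200/2 = 100 mg = 2 × 50
- 600/2 = 300 mg = 4 × 75

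Every total can be made, so the strengths do not discriminate.

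**Step 5. Does Section 1.2 decide?** 2 × 200 = 400 mg/day and 2 × 300 = 600 mg/day.

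- Group 3: both doses fit under 600 and neither fits under 200. This supports the Summary.
- Group 2: both exceed the agreed 200.
- Group 4: both exceed 150 and 200.

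Read as covering all combinations, the sentence contradicts even the undisputed Group 2 ceiling. It cannot settle the matter, and it is a third dose statement in need of correction.

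**Step 6. Signs of which list is newer.** Section 6.2 still describes a twenty-four-week treatment period, while Section 3 allows up to 48 weeks. The Summary is also internally regular: 600 mg in both groups without Norvir, and 200 mg or less in both groups with it. Section 6.2 breaks that pattern in Group 3. On the other side, Section 6 was at least partly updated, because Sections 6.9 and 6.10 run to Week 48 and Visit 19.

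**The case against.** The strongest reply is that this is a consistency error with little effect on the trial's results. Much of that stands.

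**Exposure.** A reader might infer that the EBP-994 exposure behind the by-group results, such as withdrawals due to adverse events (Section 8.4.1), is unknown for Groups 3 and 4. The documents do not support that. Subjects keep a diary of date, time and capsule count (Section 6.2), containers are returned and checked (Section 5.4), and administration goes into the accountability record (Section 5.5). Those results can be read against recorded doses.

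**Bias.** A reader might infer a biased treatment comparison. Section 8.6 plans viral-load listings, graphs, means and medians, with no between-group test, so no planned comparison is affected.

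**Safety margin.** Neither Group 3 figure exceeds the maximally tolerated dose in Section 1.2 (2 × 300 = 600 mg/day), and the higher Group 4 figure equals the undisputed Group 2 ceiling. This is fair but limited: that tolerated dose is not shown for use with Pegasys, and Group 2 does not receive Pegasys.

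**The Summary is plainly right.** Step 6 and Section 1.2 make this tempting for Group 3. They are indications, not a rule of precedence, and for Group 4 Section 1.2 supports neither figure.

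**Use the lower figure meanwhile.** The resulting set, 600/200/200/150, appears on neither page. It would exclude from Group 3 both doses named in Section 1.2. If 200 mg/day is given as 100 mg BID, it is the dose about which Section 1.1 says "suboptimal levels of drug appear to be achieved in this patient population at the relatively low dose (100 mg PO BID". That remark concerns EBP-994 alone, so it does not show that 600 mg is right with Pegasys, but it does show that the lower figure is not a neutral default.

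None of this removes the conflict in the permitted dose.

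**Conclusion.** Wrong as written. The protocol gives two current and incompatible EBP-994 ceilings for Group 3 (600 and 200 mg/day, 3-fold) and for Group 4 (150 and 200 mg/day, 1.33-fold), and no text says which governs. Group 3 carries most of the weight. The case for correction rests on the permitted dose alone, because the site cannot follow both pages over the ranges in step 2.

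The documents favour the Summary's 600 mg for Group 3 without proving it, and they leave Group 4 open. The conclusion assumes that both lists are in force, which is how they are presented, and that no randomisation or pharmacy document outside this protocol overrides them. The protocol refers to none.

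**What to change.** By one amendment under Section 14:

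1. The sponsor confirms one EBP-994 daily maximum for Group 3 and one for Group 4.
2. Each is stated identically in the Protocol Summary (Study Design) and in Section 6.2 item 6.
3. The Section 1.2 sentence on 200 vs 300 mg BID is limited to the groups it applies to. As it stands it cannot cover Group 2 or Group 4, and it covers Group 3 only if 600 mg is confirmed.

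The cost is a wording change in three places, submission to the regulatory authorities, and IRB/EC approval before it takes effect. It needs no extra subjects, visits or assays.
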